However, in this ARISTOTLE sub-group analysis, subjects who underwent cardioversion had already been chronically anticoagulated either prior to entry or, if treatment-naïve, as part of the trial. Thus, there was no information on the effectiveness of apixaban in subjects newly presenting with AF who were anticoagulant-naïve and in whom an early cardioversion was indicated, eg, with an image-guided approach or a definite onset of symptoms ≤48 hours. An image-guided approach facilitates cardioversion earlier than the conventional minimum of 3 weeks of anticoagulation that would normally be required prior to cardioversion. It is expected that most image-guided cardioversions would occur from a few hours to a few days after initial presentation. In subjects with a clearly defined onset of symptoms ≤48 hours, guidelines suggest that cardioversion may be performed early without image-guidance.

Therefore, this study is being conducted to assess the effectiveness of apixaban compared with usual care (parenteral heparin and/or oral anticoagulation with Vitamin K antagonist (excluding other novel oral anticoagulants (NOACs)) in subjects with non-valvular AF indicated for early cardioversion and initiation of anticoagulation in a real-world, clinical practice setting. The image guidance approach in subjects with >48 hours or unknown duration and non-guided with symptoms ≤48 hours will be referred to as “early

cardioversion” throughout this protocol. Subjects with symptom onset >48 hours or unknown duration and not following an image guided approach are expected to receive the conventional anticoagulation strategy (minimum of 3 weeks prior to cardioversion) as per guidelines.

The overriding design principle of this study is that of a randomized observational approach, sometimes known as a ‘pragmatic study’, where subjects are managed according to their investigator’s usual care following randomization, and in conjunction with the protocol directed schedule of activities.

Data from 15 completed or on-going Phase 2/3 studies in over 29,000 subjects provide exposure information of apixaban doses ranging from 2.5 mg twice a day (BID) to 20 mg once daily (QD) and treatment durations up to approximately 33 months.

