5.1. Full Analysis Set

The Full Analysis Set contains all randomized subjects. It will be used under the intent to treat principle (subjects will be categorized to the treatment group to which they were assigned by the IVRS, regardless of the treatment actually received).

5.2. 'Per Protocol' Analysis Set

N/A

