5.4. Other Analysis Sets

Prevention-evaluable analyses datasets will be created in order to exclude subjects identified at visit 2 through imaging as already having a thrombus; if multiple evaluations took place over time for a subject, only the first one will be used.

The Full Prevention-Evaluable Analysis Set is obtained by excluding thrombus-positive subjects from the Full Analysis Set. The Safety Prevention-Evaluable Analysis Set is obtained by removing subjects with thrombus from the Safety Analysis Set. The sets of Thrombus Positive-Full Analysis Set and Thrombus Positive-Safety are the complements of the Full Prevention-Evaluable and Safety Prevention-evaluable subjects.

The Modified Full Analysis Set is the subset of the Full Analysis Set of subjects that received at least one study drug dose.

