Routine hemoglobin and serum creatinine will be recorded within the CRF from Visit 1 to Visit 3. The data will be presented in listings without imputations and displaying even multiple findings per visit. The lab data will not be summarized.

Compliance for apixaban will be reported and summarized overall. The compliance formula is: $\# \text{tablets taken} / (\# \text{of days} * 2 + L)$ where $L=1$ if loading dose was given and 0 otherwise.

INR will be summarized for the usual care arm. Rosendaal's linear interpolation methodology will be used to determine the proportion of time in specified INR range and time to therapeutic range (i.e. time from randomization to the first INR greater than or equal to 2).

Time to withdrawal will be analyzed and displayed as a KM figure.

For the adjudicated TEEs, we will report the concordance/discordance between investigator's assessment and the adjudicator's assessment, without regard to treatment arm. Details of the adjudicated TEEs will be included in a listing, as well as details of the investigator's initial TEE assessment.

Demogs/baseline characteristics will be summarized for the following groups: 10 mg load vs no load, 5 mg load vs. no load, 10 mg load vs 5 mg load

Demogs/baseline characteristics will be compared for spontaneous vs. interventional cardioversion within the Apixaban arm.

Demogs/baseline characteristics will be compared for spontaneous vs. interventional cardioversion within the usual care arm.

Demogs/baseline characteristics will be compared for spontaneous vs. interventional cardioversion in the two treatment arms combined.

Demogs/baseline characteristics will be compared for electrical vs. pharmacological vs. both cardioversion within the Apixaban arm.

Demogs/baseline characteristics will be compared for electrical vs. pharmacological vs. both cardioversion within the usual care arm.

Demogs/baseline characteristics will be compared for electrical vs. pharmacological vs. both cardioversion in the two treatment arms combined.

Demogs/baseline characteristics will be compared for subjects with thrombus vs. subjects without thrombus.

The following analyses/comparisons will be performed for each of the clinical endpoints; the Full Analysis Set will be used for stroke, systemic embolism, and for death, while the safety dataset will be used for the bleeding endpoints;

for the following Apixaban groups: 10 mg load vs no load, 5 mg load vs. no load, 10 mg load vs 5 mg load

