for spontaneous vs. interventional cardioversion within the Apixaban arm.

for spontaneous vs. interventional cardioversion within the usual care arm.

for spontaneous vs. interventional cardioversion in the two treatment arms combined.

for electrical vs. pharmacological vs. both cardioversion within the Apixaban arm.

for electrical vs. pharmacological vs. both cardioversion within the usual care arm.

for electrical vs. pharmacological vs. both cardioversion in the two treatment arms combined.

for subjects with thrombus vs. subjects without thrombus.

References

N/A

APPENDICES

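### SAP 8.2.5 does not define subjects without thrombus; under the only classification in the SAP, that group includes subjects who were never imaged

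*SAP*

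**What the plan says.** SAP 8.2.5 (Other analyses) contains the contrast twice. For baseline: "Demogs/baseline characteristics will be compared for subjects with thrombus vs. subjects without thrombus". For each clinical endpoint, the last item in its list of comparisons is "for subjects with thrombus vs. subjects without thrombus". On the data for the endpoint list, it says "the Full Analysis Set will be used for stroke, systemic embolism, and for death", with the safety dataset for bleeding. SAP 5.1 adds: "The Full Analysis Set contains all randomized subjects".

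SAP 8.2.5 does not define the group without thrombus. The classification comes from SAP 5.4, whose purpose is to "exclude subjects identified at visit 2 through imaging as already having a thrombus". If a subject had several evaluations, only the first counts. Then: "The Full Prevention-Evaluable Analysis Set is obtained by excluding thrombus-positive subjects from the Full Analysis Set". The safety version is built in the same way, and the thrombus-positive sets "are the complements of the Full Prevention-Evaluable and Safety Prevention-evaluable subjects". SAP 8.2.4 repeats the scheme and specifies the investigator's assessment. Appendix 1.2, where sets could be refined, is marked not applicable.

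Protocol 1.2 describes who is imaged. For a clearly defined onset within 48 hours, it notes that under the guidelines "cardioversion may be performed early without image-guidance". Early cardioversion with image guidance is described for AF of more than 48 hours or unknown duration. Subjects with such AF who do not follow the image-guided route are expected to have at least 3 weeks of anticoagulation first.

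**The concern.** A subject can be thrombus-positive only if imaged. If the reference group is everyone else, it pools two kinds of subject: those imaged with no thrombus found, and those never imaged, in whom a thrombus may have been present and gone undetected. Imaging is not randomized; it follows AF duration and the chosen strategy. The contrast therefore compares a group that is entirely imaged with one that is only partly imaged, and differences between imaged and non-imaged subjects would be read as features of thrombus.

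The baseline table is where this matters most. Duration of arrhythmia is one of the baseline variables of interest in SAP 6.4 and also drives the decision to image. It could differ between the two columns even if it were unrelated to thrombus among imaged subjects. That does not depend on the number of outcome events.

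**Working it through.** The plan states no figure on this point, so there is none to reproduce. The check has two parts.

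**1. Applying the definitions**

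- The endpoint contrasts start from the Full Analysis Set, which is all randomized subjects (SAP 5.1), or from the safety dataset.
- Thrombus-positive requires a positive image (SAP 5.4, 8.2.4).
- The two classes are complements (SAP 5.4), so a never-imaged subject falls in the class without thrombus. There is no third class.
- Never-imaged subjects are expected. Protocol 1.2 describes two non-imaged routes, SAP 8.2.5 compares time to first cardioversion attempt between image-guided and non-image-guided subjects, and SAP 8.2.4 makes image guidance a subgroup.

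**2. Illustrating the possible size**

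Input from the documents: N = 1500 (Protocol 9.1). Assumptions, because the documents give no values:

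- f, the fraction imaged, from 30% to 90%;
- t, thrombus prevalence among the imaged, 5%;
- r, the ratio of endpoint risk in imaged to never-imaged subjects, 2 or 0.5.

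Formulas:

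- imaged-positive = N f t; imaged-negative = N f (1 − t); not imaged = N (1 − f)
- share of the reference group never imaged = (1 − f) / (1 − f t)
- risk ratio shown when thrombus has no effect among imaged subjects = [f(1 − t) + (1 − f)] / [f(1 − t) + (1 − f)/r]

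Example at f = 50%: share = 0.5 / 0.975 = 51%. With r = 2, the risk ratio is (0.475 + 0.5) / (0.475 + 0.25) = 0.975 / 0.725 = 1.34.

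| Imaged (f) | Imaged-positive | Imaged-negative | Not imaged | Reference group as defined | Share not imaged | RR shown, r = 2 | RR shown, r = 0.5 |
|---|---|---|---|---|---|---|---|
| 30% | 22.5 | 427.5 | 1050 | 1477.5 | 71% | 1.55 | 0.58 |
| 50% | 37.5 | 712.5 | 750 | 1462.5 | 51% | 1.34 | 0.66 |
| 70% | 52.5 | 997.5 | 450 | 1447.5 | 31% | 1.18 | 0.76 |
| 90% | 67.5 | 1282.5 | 150 | 1432.5 | 10% | 1.06 | 0.91 |

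The shares hardly depend on t. Over t = 3% to 10% they run 71–72%, 51–53%, 31–32% and 10–11%.

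If the reference group is imaged-negative subjects only, the never-imaged share is 0 and, under the same null, the risk ratio is 1.00 in every row.

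**The case against.** The best counter-argument is that SAP 8.2.5 never says never-imaged subjects count as having no thrombus. Naming the Full Analysis Set does not mean that every member is classified: the loading-dose, spontaneous versus interventional, and electrical versus pharmacological contrasts in the same list each use only part of it. An imaged-only reading is therefore not excluded. This stands as a limit on the claim. But no set in the SAP supports that reading, and SAP 5.4 uses the same term, subjects with thrombus, to form the complement. The definition has to be written under either reading.

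Part of the problem is already covered. Image guidance is a subgroup for the clinical endpoints, the thrombus-positive sets are analysed separately, and arrhythmia duration is a covariate in the Cox models. If the imaging definitions align, imaged-negative endpoint counts could be obtained by subtraction. That reduces the loss for endpoints. It does not repair the baseline table, and the covariate models do not include the thrombus contrast.

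The stakes are also low. The study is descriptive, and Protocol 9.1 predicts 4 strokes or systemic emboli (1 + 3) and 7 major bleeds (2 + 5) in total. An endpoint contrast by thrombus status would say little with either reference group.

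Two stronger readings are tempting. A reader might infer that the SAP declares never-imaged subjects free of thrombus, so that the prevention-evaluable sets are wrong. SAP 5.4 only removes known positives. Keeping the never-imaged there stays close to intention to treat and is defensible as a sensitivity analysis. A reader might also want a prevention-evaluable set limited to imaged-negative subjects. Comparing arms in such a set would condition on an investigator's choice made after open-label randomization, which brings in selection.

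**Conclusion.** The point holds as a missing definition with a real consequence for one set of exploratory contrasts. Under the SAP's only classification, the reference group for thrombus includes subjects of unknown status, and because imaging tracks AF duration and strategy, the contrast mixes thrombus status with the choice to image. The baseline comparison is the most exposed.

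The size and direction cannot be determined from the documents. The table in the working rests entirely on assumed imaging rates, prevalence and risk ratios. Its results run both ways, and at 90% imaged the effect is small. It shows what could happen, not an estimate of bias.

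The documents do not support extending this to the treatment comparison. The randomized analyses in the Full Analysis Set, and the bleeding analyses in the Safety Analysis Set, do not use thrombus status and are unaffected.

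**What to change.** In SAP 8.2.5:

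- Classify each subject as imaged-positive, imaged-negative or not imaged, using the investigator's assessment at the first evaluation, as in SAP 5.4 and 8.2.4.
- Run the baseline and endpoint contrasts for thrombus among imaged subjects only, positive versus negative.
- Show the not-imaged as a separate column.

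Leave the prevention-evaluable sets as defined, with known positives removed, and report by arm how many of their members were not imaged. Do not add an imaged-negative-only set for comparing arms.

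The cost is mainly SAP wording. Use of image guidance is already recorded (Protocol 6.2), and thrombus-positive status by investigator's assessment is already needed for SAP 8.2.4, so imaged-negative follows as imaged and not positive. The documents do not say that negative readings are themselves a CRF field, so this should be confirmed before the wording is final. The downside is a smaller reference group in an exploratory analysis: under the assumptions in the working, 712.5 instead of 1462.5 if half are imaged, and 1282.5 instead of 1432.5 if 90% are.

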Appendix 1. DATA DERIVATION DETAILS

Appendix 1.1. Definition of Protocol Deviations that Relate to Statistical Analyses/Populations

N/A

Appendix 1.2. Definition of Analysis Populations/Sets

N/A

Appendix 1.3. Further Definition of Endpoints

N/A

Appendix 2. STATISTICAL METHODOLOGY DETAILS

N/A

Appendix 2.1. Further Details of Interim Analyses

N/A

Appendix 2.2. Further Details of the Statistical Methods

N/A
